9 ADVERSE EVENTS

This is a low-risk study. Participants found to have a PHQ9 score of >20 will be told of the result and asked if their GP can be informed of the finding to arrange appropriate follow-up and management.

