3 STUDY DESIGN

The HeadOn feasibility study is a prospective feasibility study of patients presenting to the Edinburgh Royal Infirmary and St John's Hospital Emergency Departments (ED) (**Figure 1**). Patients will be identified from the ED. Potentially eligible patients will be contacted by a member of the Emergency Medicine Research Group Edinburgh (EMERGE) research team and their consent will be sought for participation. Those not recruited at presentation to the ED will be contacted by telephone, text or email within two weeks of their concussion date to seek their participation in the study, again by a member of the EMERGE research team. After consenting, the participant will be taken through the registration process for the HeadOn program. For patients who are contacted after discharge they will be taken through registration process over the telephone or if preferable will be able to return to the ED to go over the process.

At registration the participant will be invited to complete a series of patient reported measures including the Rivermead post-concussion questionnaire, Pittsburgh Sleep Quality Index, PHQ9 questionnaire and FAST alcohol questionnaire within the HeadOn program. Alongside this, a series of researcher-led anonymised data points will be collected in a separate specially designed database including demographics, date of concussion, neurological and imaging findings which will all be collected from the medical notes and imaging reports. The HeadOn program runs for five weeks following which the participant will be invited to complete the same set of outcome measures. Alongside this, all the participant will be contacted (via telephone, text or email) by a member of the research team at week 5 to complete a further five measurements: Glasgow Outcome Score Extended, mHealth App Usability questionnaire, time to return to work and a healthcare utility questionnaire. Interested participants will be invited back within two months of enrolling in the study for a more detailed qualitative interviews about HeadOn. The study will recruit for a period of 6-months or up to 100 participants.

[figure not shown]

Figure 1: Schematic of HeadOn study design

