6. DATA COLLECTION

Data will be collected at four points during the study period: at baseline, during the HeadOn program, at the final 5-week follow-up and during a voluntary qualitative interview. Two forms of data will be collected: patient-reported and researcher collected.

At baseline, participants will complete four patient questionnaires within the HeadOn program (Rivermead postconcussion, PHQ9, Pittsburgh Sleep Quality and the FAST alcohol screen). Researchers will also capture demographic, clinical and imaging findings data taken from participants notes and investigation finding reports. During the HeadOn program, participants will undergo a series of ecological momentary assessments (EMAs) aimed at capturing information about their symptoms, mood, thoughts about their concussion and behaviour (**Appendix**). This includes a symptom and mood diary which will be delivered daily. Alongside this, a series of other EMAs are delivered to the participant at different stages of the program (**Figure 2**): Stage 3 (Alcohol tracker), Stage 4 (Thought diary) and Stage 5 (Goal setting). HeadOn generates automated reminders (by email or notification) to help keep participants engaged. In the final 5-week follow-up of the study, both participant-reported and researcher collected outcome measures will be captured. Participants will complete the following questionnaires digitally through the HeadOn program: Rivermead postconcussion, PHQ9, Pittsburgh Sleep Quality and FAST alcohol screen. The participant will also be contacted by a trained member of the HeadOn research team to complete four questionnaires: the mHealth app usability questionnaire, healthcare utility, return to work questionnaire and the Glasgow Outcome Score Extended (GOSE). The participant will also be reminded to complete the week 5 patient-reported questionnaires if they had not already done so. If the participant has not completed these questionnaires by week 6, then they will be contacted again by a member of the research team to complete these questionnaires.

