Appendix I: Rivermead Post-concussion Questionnaire

PATIENT HEALTH QUESTIONNAIRE - 9				
Over the last 2 weeks, how often have you been bothered by any of the following problems?	Not at all	Several days	More than half the days	Nearly every day
1. Little interest or pleasure in doing things	0	1	2	3
2. Feeling down, depressed, or hopeless	0	1	2	3
3. Trouble falling or staying asleep, or sleeping too much	0	1	2	3
4. Feeling tired or having little energy	0	1	2	3
5. Poor appetite or overeating	0	1	2	3
6. Feeling bad about yourself — or that you are a failure or have let yourself or your family down	0	1	2	3
7. Trouble concentrating on things, such as reading the newspaper or watching television	0	1	2	3
8. Moving or speaking so slowly that other people could have noticed? Or the opposite — being so fidgety or restless that you have been moving around a lot more than usual	0	1	2	3
9. Thoughts that you would be better off dead or of hurting yourself in some way	0	1	2	3
FOR OFFICE CODING ____ + ____ + ____ + ____ =Total Score: _____				

If you checked off any problems, how difficult have these problems made it for you to do your work, take care of things at home, or get along with other people?

Not difficult at all 	Somewhat difficult 	Very difficult 	Extremely difficult 
---	---	---	--

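### The only stated safety action needs a PHQ9 total above 20, so a positive answer to the self-harm item can pass with no stated response

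*Combined protocol and SAP*

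**What the plan says.** Section 9 (Adverse Events) describes the study as low risk and then gives a single action on participants' answers: "Participants found to have a PHQ9 score of >20 will be told of the result and asked if their GP can be informed". No other cut-off, item or response is mentioned there.

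The PHQ-9 form in the Appendix has nine items, each scored 0 to 3. Item 9 reads "Thoughts that you would be better off dead or of hurting yourself in some way".

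The form is offered at baseline and at week 5.

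- **Baseline.** Section 3 says "After consenting, the participant will be taken through the registration process for the HeadOn program", and then "At registration the participant will be invited to complete a series of patient reported measures". Section 6 places the baseline PHQ9 inside the app.
- **Week 5.** Section 6 says "Participants will complete the following questionnaires digitally through the HeadOn program: Rivermead postconcussion, PHQ9" and two further measures. Section 3 adds that "all the participant will be contacted (via telephone, text or email) by a member of the research team at week 5". Section 6 continues: "The participant will also be reminded to complete the week 5 patient-reported questionnaires if they had not already done so". It also says: "If the participant has not completed these questionnaires by week 6, then they will be contacted again by a member of the research team".

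No visible section attaches an action to a positive item 9 answer, or to any PHQ9 total of 20 or less.

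**The concern.** A total score and a self-harm item answer different questions. The total measures overall depressive burden; item 9 asks directly about thoughts of death or self-harm. When the only trigger is a high total, someone can report such thoughts nearly every day and still fall below it, while someone who reports none can exceed it.

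The study invites each participant to answer this item up to twice, in an app, with no stated check of the single answer. Section 1.1 says that concussion can bring emotional symptoms, and Section 4.3 does not exclude people with current depression or self-harm thoughts. Staff who follow Section 9 to the letter would have no instruction to contact a participant, give feedback or offer to inform the GP on the strength of item 9. Any response would depend on someone happening to see the answer and choosing to act.

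**Working it through.** **Inputs.** The trigger is a PHQ9 total above 20, so 21 or more (Section 9). There are nine items scored 0 to 3, so the maximum is 9 × 3 = 27 (PHQ-9 form, Appendix). The cut-off is stated without a derivation, so there is no planned figure to reproduce.

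**What the rule needs when item 9 is positive.** Required sum of items 1 to 8 = 21 − item 9 score, out of a maximum of 8 × 3 = 24.

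| Item 9 score | Sum of the other eight needed to trigger | No stated action at or below |
|---|---|---|
| 1 | 20 | 19 |
| 2 | 19 | 18 |
| 3 | 18 | 17 |

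**Example profiles.**

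- Item 9 = 3, other eight at 2: 8 × 2 + 3 = 19. No action.
- Item 9 = 3, one of the eight at 3, seven at 2: 7 × 2 + 3 + 3 = 20. No action, because the rule is strict.
- Item 9 = 3, two of the eight at 3, six at 2: 6 × 2 + 2 × 3 + 3 = 21. Action.
- Item 9 = 0, five items at 3, three at 2: 5 × 3 + 3 × 2 + 0 = 21. Action.

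**All patterns.** The other eight items can be answered in 4^8 = 65,536 ways. With item 9 = 3, 62,893 of these (96%) give a total of 20 or less; with item 9 = 2, 64,321 (98%); with item 9 = 1, 65,049 (99%). These count score combinations. They are not estimates of how often patients would give such answers.

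**Whether scheduled contacts close the gap.**

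- *Registration.* Staff are involved when the baseline form is offered, but no text says that they look at the answers. The next stated staff contact for all participants is at week 5: 5 × 7 = 35 days later.
- *Week 5.* This contact may be by telephone, text or email, and no self-harm content is described. It can come before the form is completed, since staff remind those who have not yet done it. A form completed after it has no later stated contact for all participants.
- *Week 6.* This contact reaches only those whose questionnaires are still outstanding.
- *Other contacts.* App reminders are automated and serve engagement (Section 6). The interview is voluntary.

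**The case against.** The strongest reply is that the gap is in visible text only. The participant information and consent pages were not available, and the app homepage (Appendix VII) has an SOS icon whose purpose is not described. Either might say what happens after a worrying answer. This stands, and it limits the conclusion to what the visible protocol states.

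Second, Section 9 sets a minimum and does not bar action at lower totals. The research team is trained and may be part of the clinical care team (Section 5.1), and Section 12.7 refers to the sites' duty of care. That is true, but none of these tells anyone to look at item 9. The duty-of-care wording concerns liability.

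Third, staff may be present when the baseline form is completed, and the existing rule implies some score-driven contact outside the schedule. So 35 days is the interval between stated contacts for all participants. It is not a period in which contact is impossible, and it should be read that way. Similarly, the week-6 contact could mean completing the forms together with staff, but only for non-completers.

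Fourth, the documents give no clinical standard for item 9, so a cut-off of 1 is a proposal. That also stands. Finally, the existing rule names neither a reviewer nor a time limit, so adding both for item 9 alone would be uneven. That is a fair point for the drafting.

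**Conclusion.** The concern holds. As visible, the protocol states no contact, feedback or GP offer prompted by a positive item 9 answer when the total is 20 or less. This includes the highest possible item 9 answer whenever the other eight items sum to 17 or less of 24. The rule can act on a participant who reports no self-harm thoughts and stay silent on one who reports them nearly every day.

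The number of participants affected cannot be computed from the documents. The primary endpoints and planned analyses are unchanged. This should be fixed on safety grounds, with moderate confidence because the consent material and the SOS function could not be examined.

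**What to change.** Keep the existing rule and add to Section 9:

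- A delegated member of the research team checks item 9 on each completed PHQ9, at baseline and week 5, within a time that the clinical lead sets and states.
- Any score of 1 or more leads to contact with the participant and the existing GP offer, or a more urgent response set by the clinical lead, whatever the total. The value 1 is a default, being the lowest non-zero answer on the form (several days); the clinical lead may state another.
- The same named reviewer and time limit can sensibly serve the existing total-score rule.

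First confirm that staff can see single item answers promptly. If the consent pages or the SOS function already cover this, a cross-reference in Section 9 is enough.

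**Cost.** One amendment, with sponsor, REC and local R&D review (Section 12.1). With full recruitment and complete forms, there are at most 100 × 2 = 200 checks over about 26 + 6 = 32 weeks, so 200 / 32 = 6.25 a week. At an assumed 2 to 5 minutes each, that is 200 × 2 / 60 = 6.7 to 200 × 5 / 60 = 16.7 staff hours. The EMERGE research nurses are already listed with access to the app data (Section 7.1, Table 2).

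Follow-up conversations are extra: 10, 20 or 40 if an assumed 5%, 10% or 20% of 200 forms are positive. So is staff cover to meet the stated time. Exported data carry only study IDs, so working from an export means re-linking through the study key. If item answers cannot be seen as they are entered, app work may be needed, and its cost cannot be estimated from the documents.

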10 OVERSIGHT ARRANGEMENTS

10.1 INSPECTION OF RECORDS

Investigators and institutions involved in the study will permit trial related monitoring and audits on behalf of the sponsor, REC review, and regulatory inspection(s). In the event of audit or monitoring, the Investigator agrees to allow the representatives of the sponsor direct access to all study records and source documentation. In the event of regulatory inspection, the Investigator agrees to allow inspectors direct access to all study records and source documentation.

10.2 STUDY MONITORING AND AUDIT

The ACCORD Sponsor Representative will assess the study to determine if an independent risk assessment is required. If required, the independent risk assessment will be carried out by the ACCORD Quality Assurance Group to determine if an audit should be performed before/during/after the study and, if so, at what frequency.

Risk assessment, if required, will determine if audit by the ACCORD QA group is required. Should audit be required, details will be captured in an audit plan. Audit of Investigator sites, study management activities and study collaborative units, facilities and 3rd parties may be performed.

11 GOOD CLINICAL PRACTICE

11.1 ETHICAL CONDUCT

The study will be conducted in accordance with the principles of the International Conference on Harmonisation Tripartite Guideline for Good Clinical Practice (ICH GCP).

Before the study can commence, all required approvals will be obtained and any conditions of approvals will be met.

11.2 INVESTIGATOR RESPONSIBILITIES

The Investigator is responsible for the overall conduct of the study at the site and compliance with the protocol and any protocol amendments. In accordance with the principles of ICH GCP, the following areas listed in this section are also the responsibility of the Investigator. Responsibilities may be delegated to an appropriate member of study site staff.

11.2.1 Informed Consent

The Investigator is responsible for ensuring informed consent is obtained before any protocol specific procedures are carried out. The decision of a participant to participate in clinical research is voluntary and should be based on a clear understanding of what is involved.

Participants must receive adequate oral and written/electronic information – appropriate Participant Information and Informed Consent Forms will be provided. The oral explanation to the participant will be performed by the Investigator or qualified delegated person, and must cover all the elements specified in the Participant Information Sheet and Consent Form.

The participant must be given every opportunity to clarify any points they do not understand and, if necessary, ask for more information. The participant must be given sufficient time to consider the information provided. It should be emphasised that the participant may withdraw their consent to participate at any time without loss of benefits to which they otherwise would be entitled.

The participant will be informed and agree to their medical records being inspected by regulatory authorities and representatives of the sponsor(s).

The Investigator or delegated member of the trial team and the participant will sign and date the Informed Consent Form(s) to confirm that consent has been obtained. The participant will receive a copy of this document and a copy filed in the Investigator Site File (ISF) and participant's medical notes (if applicable).

11.2.2 Study Site Staff

The Investigator must be familiar with the protocol and the study requirements. It is the Investigator's responsibility to ensure that all staff assisting with the study are adequately informed about the protocol and their trial related duties.

11.2.3 Data Recording

The Principal Investigator is responsible for the quality of the data recorded in the CRF at each Investigator Site.

11.2.4 Investigator Documentation

- The Principal Investigator will ensure that the required documentation is available in local Investigator Site files ISFs.

11.2.5 GCP Training

For non-CTIMP (i.e. non-drug) studies all researchers are encouraged to undertake GCP training in order to understand the principles of GCP. However, this is not a mandatory requirement unless deemed so by the sponsor. GCP training status for all investigators should be indicated in their respective CVs.

11.2.6 Confidentiality

All laboratory specimens, evaluation forms, reports, and other records must be identified in a manner designed to maintain participant confidentiality. All records must be kept in a secure storage area with limited access. Clinical information will not be released without the written permission of the participant. The Investigator and study site staff involved with this study may not disclose or use for any purpose other than performance of the study, any data, record, or other unpublished information, which is confidential or identifiable, and has been disclosed to those individuals for the purpose of the study.. Prior written agreement from the sponsor or its designee must be obtained for the disclosure of any said confidential information to other parties.

11.2.7 Data Protection

All Investigators and study site staff involved with this study must comply with the requirements of the appropriate data protection legislation (including the General Data Protection Regulation and Data Protection Act) with regard to the collection, storage, processing and disclosure of personal information.

Computers used to collate the data will have limited access measures via user names and passwords.

Published results will not contain any personal data and be of a form where individuals are not identified and re-identification is not likely to take place

12 STUDY CONDUCT RESPONSIBILITIES

12.1 PROTOCOL AMENDMENTS

Any changes in research activity, except those necessary to remove an apparent, immediate hazard to the participant in the case of an urgent safety measure, must be reviewed and approved by the Chief Investigator.

Amendments will be submitted to a sponsor representative for review and authorisation before being submitted in writing to the appropriate REC, and local R&D for approval prior to participants being enrolled into an amended protocol.

12.2 MANAGEMENT OF PROTOCOL NON-COMPLIANCE

Prospective protocol deviations, i.e. protocol waivers, will not be approved by the sponsors and therefore will not be implemented, except where necessary to eliminate an immediate hazard to study participants. If this necessitates a subsequent protocol amendment, this should be submitted to the REC, and local R&D for review and approval if appropriate.

Protocol deviations will be recorded in a protocol deviation log and logs will be submitted to the sponsors every 3 months. Each protocol violation will be reported to the sponsor within 3 days of becoming aware of the violation. All protocol deviation logs and violation forms should be emailed to [contact]

Deviations and violations are non-compliance events discovered after the event has occurred. Deviation logs will be maintained for each site in multi-centre studies. An alternative frequency of deviation log submission to the sponsors may be agreed in writing with the sponsors.

12.3 SERIOUS BREACH REQUIREMENTS

A serious breach is a breach which is likely to effect to a significant degree:

- (a) the safety or physical or mental integrity of the participants of the trial; or
- (b) the scientific value of the trial.

If a potential serious breach is identified by the Chief investigator, Principal Investigator or delegates, the co-sponsors ([contact]) must be notified within 24 hours. It is the responsibility of the co-sponsors to assess the impact of the breach on the scientific value of the trial, to determine whether the incident constitutes a serious breach and report to research ethics committees as necessary.

12.4 STUDY RECORD RETENTION

All study documentation will be kept for a minimum of 3 years from the protocol defined end of study point. When the minimum retention period has elapsed, study documentation will not be destroyed without permission from the sponsor.

12.5 END OF STUDY

The end of study is defined as the last participant's last visit.

The Investigators or the co-sponsor(s) have the right at any time to terminate the study for clinical or administrative reasons.

The end of the study will be reported to the REC, and R+D Office(s) and co-sponsors within 90 days, or 15 days if the study is terminated prematurely. The Investigators will inform participants of the premature study closure and ensure that the appropriate follow up is arranged for all participants involved. End of study notification will be reported to the co-sponsors via email to [contact]

A summary report of the study will be provided to the REC within 1 year of the end of the study.

12.6 CONTINUATION OF TREATMENT FOLLOWING THE END OF STUDY

Once the study is completed, patient access to the HeadOn site will be restricted to allow analysis of the data and the integration of any development changes to the program.

12.7 INSURANCE AND INDEMNITY

The co-sponsors are responsible for ensuring proper provision has been made for insurance or indemnity to cover their liability and the liability of the Chief Investigator and staff.

The following arrangements are in place to fulfil the co-sponsors' responsibilities:

- The Protocol has been designed by the Chief Investigator and researchers employed by the University and collaborators. The University has insurance in place (which includes no-fault compensation) for negligent harm caused by poor protocol design by the Chief Investigator and researchers employed by the University.
- Sites participating in the study will be liable for clinical negligence and other negligent harm to individuals taking part in the study and covered by the duty of care owed to them by the sites concerned. The co-sponsors require individual sites participating in the study to arrange for their own insurance or indemnity in respect of these liabilities.
- Sites which are part of the United Kingdom's National Health Service will have the benefit of NHS Indemnity.
- Sites out with the United Kingdom will be responsible for arranging their own indemnity or insurance for their participation in the study, as well as for compliance with local law applicable to their participation in the study.

